#### **10.1.4 Laboratory safety assessments**

Changes from baseline to visit 3 for all patients will be calculated as the post-baseline test value minus the baseline test value. Laboratory test results will also be compared with the laboratory reference ranges, and values that are outside the applicable reference range will be flagged at high or low.

#### **10.1.5 ECG**

Changes from baseline to visit 3 for ECG interval data and rate data will be derived by subtracting the baseline value from the final assessment data. Marked abnormal values or changes from baseline will be identified based on pre-determine criteria.

#### **10.1.6 Vital Signs**

Changes from baseline in vital signs (sitting blood pressure, pulse, and respiratory rate) at post baseline (Visits 2, 3, and 4) will be derived as the value at the visit minus the baseline value for the same assessment.

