|   | Consenting/Screening (followed by $\geq$ 7 day baseline data) | Begin Double Blind Treatment      | Completion of RCT/Begin Open Label Treatment | End of Open-label Phase            |  |
|   | day -8  | day 1 (+ $\leq$ 3 days if needed) | day 15 (+ $\leq$ 3 days if needed)           | Day 29 (+ $\leq$ 3 days if needed) | Telephone Contact after 7 days (+ $\leq$ 3 days) |
| Informed Consent  | X   |                                   |  |                                    |  |
| Inclusion and Exclusion                                   | X   |                                   |  |                                    |  |
| Demographic Information                                   | X   |                                   |  |                                    |  |
| Medical History   | X   |                                   |  |                                    |  |
| Complete Physical Exam                                    | X   |                                   |  |                                    |  |
| Brief Physical Exam                                       |   |                                   | As needed                                    |                                    |  |
| Palliative Performance Scale                              | X   |                                   |  |                                    |  |
| Vital Signs & Weight                                      | X   | X (no weight)                     | X (no weight)                                | X (no weight)                      |  |
| Perform or Review 12 lead ECG                             | X   |                                   | X  |                                    |  |
| Blood Sample Collection (CMP, ALT, AST & CBC) (Local Lab) | X   |                                   | X  |                                    |  |
| Urine Pregnancy Test (WOCP)                               | X   |                                   |  |                                    |  |
| Concomitant Medication Review                             | X   | X                                 | X  | X                                  |  |
| Confirm eligibility                                       |   | X                                 |  |                                    |  |
| Query change in medical status                            |   | X                                 | X  |                                    |  |

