### **3.2.2 Visit 2 – Randomization (Part 1 Double Blind Treatment Period)**

Visit 2 may take place in an office or the patient's home. It must occur within 3 days of the end of the baseline period. At Visit 2, the study coordinator will perform the following tasks:

- Review study procedures and confirm eligibility
- Review concomitant medications taken by the patient during the past 48 hours
- Measure sitting blood pressure, pulse, and respiratory rate
- Dispense study medication and instruct the patient (and caregiver, if appropriate) on daily use
- Dispense the rescue laxative and instruct the patient (and caregiver, if appropriate) on use

- Dispense the paper diary and refresh training on daily use.
- Review and record adverse events since visit 1
- Administer the first dose of double-blind study drug and record the time of the dose
- Have patient complete the following validated questionnaires: PAC-SYM, PAC-QOL, and NRS for pain
- Scheduling the next visit for approximately 14 days (+/- 3 days)

After Visit 2, patients will take one dose of study medication (naloxegol or placebo) daily for 14 days and may use rescue laxative as instructed. He or she will again complete the daily diary to capture information about study outcomes. The research coordinator may telephone the patient as needed to answer questions and encourage adherence to study procedures. The research coordinator must contact the patient at 72 hours (+/- 24 hours) after Visit 2.

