### **6.3.12 Vital signs**

Sitting blood pressure, pulse/heart rate, and respiratory rate must be measured at Visits 1, 2, 3 and 4. The patient must be resting at least 5 minutes before measurement and an appropriately sized cuff should be used. Patient's weight and temperature will be measured at the first visit. The measurements will be recorded in eCRF.

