#### **6.3.13.2 Blood pressure and heart rate measurements**

Pre-clinical investigations have included a recent dog telemetry study which demonstrated small, transient decreases in blood pressure, left ventricular systolic pressure, cardiac contractility and relaxation indices, as well as increases in heart rate, at blood concentrations about 5 times higher than the maximum dose used in this study (ie, 25 mg). While there have been isolated reports of patients with potentially clinically significant BP decreases in trials of naloxegol, such cases have also been observed with placebo. No clear or consistent cardiovascular signal has been observed in human studies to date.

Therefore, care should be taken in the measurement of heart rate and BP at all visits; for specific instructions on methods for measurement, please refer to Section 6.3.12. It should be noted that vital sign abnormalities should generally be reported as AEs only if they fulfill AE criteria proper or are the reason for discontinuation of treatment with the study drug (see Section 6.3.3).

In general, the investigator should maintain a low threshold for considering additional diagnostic tests (eg, ECGs, echocardiogram, additional orthostatic measurements, chest X-rays, etc.) as appropriate, based on clinical assessment and patient history.

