#### **11.2.1 Safety and tolerability analyses**

Adverse events will be classified by body system and preferred team and summarized by the number of patients with events per treatment group. AEs which in the opinion of the investigator are unequivocally due to the progression of a patient's underlying cancer may be analyzed and tabulated separately from other AEs. The number of TEAEs related to the study drug or probably related to the study drug will be compared across active drug and placebo. The number of these AEs mapped to the GI tract will be additionally analyzed. As noted, this analysis will be augmented by descriptive incidence data from the extension period.

The change from baseline in the mean daily opioid dose and mean NRS pain scores (average and worst per day) will be summarized by treatment group, and tested within each treatment group using one-sample t-tests.

All laboratory test results, vital signs (sitting BP and pulse), ECG results, respiratory rate, hematology and blood chemistry will be summarized for each treatment group using descriptive statistics and change from baseline.

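### Section 10.1.6 treats Visit 2, the visit at which study drug starts, as a post-baseline vital-sign outcome and does not name the baseline, which by elimination is Visit 1

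*Combined protocol and SAP*

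**What the plan says.** Section 10.1.6 plans "Changes from baseline in vital signs (sitting blood pressure, pulse, and respiratory rate) at post baseline (Visits 2, 3, and 4", and each change "will be derived as the value at the visit minus the baseline value for the same assessment". The section does not identify the baseline visit.

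Section 6.3.12 fixes the measurement schedule: "Sitting blood pressure, pulse/heart rate, and respiratory rate must be measured at Visits 1, 2, 3 and 4". Table 1 agrees and places Visit 1 on day -8, Visit 2 on day 1, Visit 3 on day 15 and Visit 4 on day 29, with up to 3 extra days allowed for each of Visits 2, 3 and 4.

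The Visit 2 task list in Section 3.2.2 contains one vital-sign entry, "Measure sitting blood pressure, pulse, and respiratory rate". Further down it has "Administer the first dose of double-blind study drug and record the time of the dose". Neither entry says when one happens relative to the other.

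Section 11.2.1 says that vital signs, with the other safety measures, "will be summarized for each treatment group using descriptive statistics and change from baseline". No test, threshold or decision rule is attached to them.

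Section 11.2.2 takes Visit 2 as the baseline for PAC-SYM and PAC-QOL.

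**The concern.** A change from baseline in a safety measure is normally read as change since treatment began. Here one of the three planned change points falls at the visit where treatment begins, so its by-arm row would sit among the safety results while saying little or nothing about the drug. The other two changes start at screening, so each mixes untreated time with time on treatment.

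The rest of the plan draws the line at the start of dosing. Treatment-emergent events count from the first dose (Section 10.1.1). The pain and opioid-dose baselines come from the confirmation period before dosing (Sections 10.1.2 and 10.1.3). Laboratory and ECG changes are taken to Visit 3 (Sections 10.1.4 and 10.1.5). Visit 2 is thus a baseline for the questionnaires and an outcome for vital signs, and no reason is given for the difference.

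Safety and tolerability are the primary aim, and Section 6.3.13.2 asks for care in measuring blood pressure and heart rate. In patients with active cancer, some drift over the run-in is plausible, and it would be reported as part of the within-group changes.

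**Working it through.** The plan gives no figure to reproduce here. The check has four steps.

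**1. Which visit is the baseline?** Vital signs exist at Visits 1, 2, 3 and 4 (Section 6.3.12 and Table 1). Section 10.1.6 labels Visits 2, 3 and 4 as post baseline. Only Visit 1 remains.

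**2. What interval does each change cover?** Inputs are the nominal days in Table 1: -8, 1, 15 and 29. The interval is the later day minus the earlier day, less 1 when crossing from negative to positive days if no day 0 is counted.

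- Visit 1 to Visit 2: 1 - (-8) = 9 days, or 8 without a day 0.
- Visit 1 to Visit 3: 15 - (-8) = 23 days, or 22.
- Visit 1 to Visit 4: 29 - (-8) = 37 days, or 36.
- Visit 2 to Visit 3: 15 - 1 = 14 days.
- Visit 2 to Visit 4: 29 - 1 = 28 days.

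| Change to | Implied baseline, Visit 1 | Of which before treatment | Baseline at Visit 2, pre-dose |
|---|---|---|---|
| Visit 2 | 8-9 days | all, if measured before the dose | none: this is the baseline |
| Visit 3 | 22-23 days | 8-9 days (8/22 = 36%, 9/23 = 39%) | 14 days, all on assigned treatment |
| Visit 4 | 36-37 days | 8-9 days (8/36 = 22%, 9/37 = 24%) | 28 days, all on treatment |

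If the run-in is extended by the permitted 3 days, its 8-9 days become 11-12. The table ignores visit windows.

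**3. Is the between-arm difference biased?** No. Write V1 and V3 for the Visit 1 and Visit 3 values. The expected difference between arms in V3 - V1 is the difference in mean V3 minus the difference in mean V1. Randomization makes the expected difference in V1 zero. The same holds for a pre-dose Visit 2 value. The choice of baseline affects the within-group changes and the precision, not the expected between-arm contrast.

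**4. How much precision is at stake?** With equal variance s² at each visit (assumed), the variance of a change is 2s²(1 - r), where r is the correlation between the two readings. Moving the baseline from Visit 1 to Visit 2 multiplies the variance of the Visit 3 change by (1 - r2)/(1 - r1). Here r1 is the correlation of Visit 3 with Visit 1, and r2 its correlation with Visit 2. The documents give neither, so these are assumptions:

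| r1 | r2 | Ratio | Reduction in variance |
|---|---|---|---|
| 0.60 | 0.60 | 0.40/0.40 = 1.00 | 0% |
| 0.68 | 0.70 | 0.30/0.32 = 0.94 | 6% |
| 0.60 | 0.65 | 0.35/0.40 = 0.875 | 12.5% |
| 0.60 | 0.70 | 0.30/0.40 = 0.75 | 25% |
| 0.60 | 0.80 | 0.20/0.40 = 0.50 | 50% |

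The result depends entirely on the gap between the two correlations. If they are equal there is no gain.

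**The case against.** The strongest reply is that Section 10.1.6 contains no internal error. With Visit 1 as baseline, Visit 2 is literally post baseline. Visit 1 is also the only scheduled point before treatment for laboratory tests and ECG, so the safety measures share a screening baseline. The vital-sign analysis is descriptive, the primary safety endpoint is the difference in adverse events (Section 10.1), and changes from Visit 2 can be computed later from data already collected. All of this stands and limits the importance of the point. It does not explain why a visit at the start of dosing should be tabulated as an outcome, or why the baseline is left unnamed.

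A reader might also infer more than the documents support:

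- *That the Visit 2 reading is certainly pre-dose.* This rests only on the order of the Section 3.2.2 list, which need not be chronological: it puts the questionnaires after the first dose, although Visit 2 is their baseline. If the reading follows the dose, the Visit 2 change includes some exposure, at a time after dosing that the plan does not define.
- *That the safety comparison is biased.* Step 3 of the working shows that it is not.
- *That the Visit 2 values dilute a summary.* Changes are derived visit by visit, and no pooling across visits is planned.
- *That a fixed gain in precision, such as 25%, is available.* It depends on correlations that the documents do not give.
- *That there is an established blood-pressure signal.* Section 6.3.13.2 does say "While there have been isolated reports of patients with potentially clinically significant BP decreases in trials of naloxegol". The same sentence adds that such cases occurred on placebo too, and the section goes on to say that human studies have shown no clear or consistent cardiovascular signal. It supports careful measurement, nothing stronger.

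**Conclusion.** The point holds as a minor defect in a stated derivation rule. The implied vital-sign baseline is Visit 1, and the planned Visit 2 change does not inform on drug effect: it is run-in change if the reading is pre-dose and has no defined exposure time if it is not. The Visit 3 and Visit 4 changes each carry 8 to 9 nominal untreated days, or 11 to 12 if the run-in is fully extended.

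The consequences are run-in drift in the within-group changes, one by-arm row open to misreading, and possibly some avoidable noise. The gain in precision from changing the baseline runs from 0% upward and cannot be fixed from the documents. No test or trial conclusion depends on this. The intervals rest on the Table 1 days. The description of Visit 2 as untreated rests on the unconfirmed assumption that the reading precedes the dose.

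**What to change.** In Section 10.1.6, define the vital-sign baseline as the last value before the first dose (Visit 2, or Visit 1 if Visit 2 is missing), and derive changes at Visits 3 and 4 only. Visit 1 values can still be listed, so the run-in remains visible.

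In Section 3.2.2, state that the Visit 2 vital signs are taken before the first dose.

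The first edit is analysis wording. The second is a one-line instruction to sites about the order of tasks already done at that visit. Neither needs a new measurement, an extra visit or more patients.

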### **10.2 Secondary aims: efficacy and feasibility**

#### **10.2.1 Calculation or derivation of efficacy variables**

The efficacy assessments of this study include the recording of daily laxation information (date and time of each SBM).

##### **10.2.1.1 SBMs Responder Rate**

A SBM is defined as a BM without rescue laxatives in the previous 24 hours. Days with no BMs should be recorded as zero, rather than missing. This diary data will be used to identify SBMs. The weekly SBM frequency within each time period will be calculated for each patient as:

(Total number of SBMs during the time period of interest/number of days) x 7,

where the denominator is the number of days during the time period in which the patient records data. If less than 4 days of data are recorded within a particular week, the data for that week will be considered insufficient and the rate will be set to missing for that week.

A responder is a patient with  $\geq 3$  SBM in a week and at least one SBM/week increase over baseline for the two weeks during which the study drug is taken. For the purposes of the analysis, the proportion of responders will be evaluated during the randomized period, and also during the extension period. The randomized period permits a comparison of response rates for those who received naloxegol and those who received placebo. The responder rate during the extension period for those patients who entered the extension period after having had placebo will be evaluated as supportive of the response rate determined during the randomized period.

#### **10.2.1.2 Time to First Laxation**

The time to first post-dose SBM will be calculated in hours as:

$$\text{Date/time of first post-dose SBM} - \text{First dose date/time}$$

Response to study drug within the first 24 hours will be assessed using the calculated time to first post-dose SBM.

#### **10.2.1.3 Days with at least 1 SBM**

The mean number of days per week with at least 1 SBM will be calculated as:

$$(\text{Total number of days with at least 1 SBM during the period of interest}/\text{number of days in the period of interest}) \times 7.$$

#### **10.2.1.4 Bristol Stool Scale**

The mean daily BSS score for an interval will be calculated as the sum of daily values for the interval divided by the number of days within the interval in which the data were collected. Change from baseline in the mean BSS score will be calculated as the post-baseline value minus the baseline value, where baseline is the mean daily BSS score recorded during the OIC confirmation period. Positive changes from baseline indicate improvement.

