### **6.2.5      Stool consistency (Bristol Stool Scale - BSS)**

Patients will rate stool consistency through completion of the BSS after each BM. The BSS is a medical aid designed to classify the form of human feces into 7 categories. It was developed by Heaton at the University of Bristol and was first published in the Scandinavian Journal of Gastroenterology in 1997 [12]. The form of the stool depends on the time it spends in the colon. The 7 stool types are:

1. Separate hard lumps, like nuts (hard to pass)
2. Sausage-shaped, but lumpy
3. Like sausage, but with cracks on its surface
4. Like a sausage or snake, smooth and soft
5. Soft blobs with clear cut edges (passed easily)
6. Fluffy pieces with ragged edges, a mushy stool
7. Watery, no solid pieces.

Types 1 and 2 indicate constipation, Types 3 and 4 represent "ideal stools," and Types 5 to 7 are tending towards diarrhea or urgency.

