#### **10.2.1.5 Degree of straining**

The mean degree of straining for an interval will be calculated as the sum of the straining values for the interval divided by the number of BMs recorded within the interval. Change from baseline in the mean degree of straining will be calculated as the post-baseline value minus the baseline value, where baseline is the mean degree of straining recorded during the OIC confirmation period. Negative changes from baseline indicated improvement.

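### The Bristol Stool Scale endpoint labels every upward change as improvement, including shifts into the diarrhea range, and leaves its daily value and denominator undefined

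*Combined protocol and SAP*

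**What the plan says.** Section 6.2.5 sets how stool form is recorded: "Patients will rate stool consistency through completion of the BSS after each BM". It assigns types 1 and 2 to constipation and calls types 3 and 4 ideal, and adds that "Types 5 to 7 are tending towards diarrhea or urgency". Type 7 is described as "Watery, no solid pieces".

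Section 10.2.1.4 derives the endpoint. The interval mean is the "sum of daily values for the interval divided by the number of days within the interval in which the data were collected", and change is taken from the 7-day OIC confirmation period. The section ends: "Positive changes from baseline indicate improvement".

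Section 10.2.1.5 handles straining, which is also rated at each BM, with a different denominator: "sum of the straining values for the interval divided by the number of BMs recorded within the interval".

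Section 10.2.1.1, which concerns counting spontaneous BMs, adds: "Days with no BMs should be recorded as zero, rather than missing". No matching rule exists for BSS.

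Section 11.2.2 summarises mean stool consistency by group and as change from baseline. It also lists BSS among the outcomes named just before the sentence that assigns t-tests to group differences.

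**The concern.** Section 6.2.5 places the target in the middle of the scale, whereas Section 10.2.1.4 places it at the top. A treatment that overshoots into loose stool would therefore earn credit on an efficacy outcome.

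Baselines from which this can happen are admissible. Section 4.1 asks for any two of five constipation symptoms, and hard stool is only one of them. A patient can enter on straining and incomplete evacuation with stools already of type 3 or 4.

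Overshoot is also foreseeable. Section 1.1 lists diarrhea among the side effects of constipation treatments, Section 5.5 allows bisacodyl rescue during treatment, and Section 10.2.1.4 does not restrict BSS to spontaneous BMs. Section 1.4 names diarrhea among the Phase II side effects of naloxegol, although in the 50 mg cohort, and this trial uses 25 mg.

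The second part is reproducibility. A programmer cannot derive the score from Section 10.2.1.4 alone when a day has no BM or several. Some of the available choices bring BM frequency into what should be a measure of form. Naloxegol is expected to raise BM frequency (Section 1.1), so under those choices any distortion would tend to favour the active arm.

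What is at stake is the stool-form effect estimate. Section 11.1 describes effect size as critical to designing the larger trial.

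**Working it through.** The plan gives no target difference, SD or power for BSS, so there is no figure to reproduce. The check applies the Section 10.2.1.4 formula to assumed 7-day diaries. The diaries are illustrations, not estimates of what patients will record.

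The text leaves two things open: how the day's ratings become one value (sum or mean), and which days are counted (all diary days or only days with a BM). That gives four readings, plus the straining form as reference:

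- A: ratings summed within the day, divided by all 7 diary days
- B: ratings summed within the day, divided by days with a BM
- C: mean rating of the day, divided by days with a BM
- D: mean rating of the day, divided by all 7 diary days
- Per BM: sum of ratings divided by number of BMs

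**Direction.** The first two rows have two BMs in the week on separate days, before and after; the third has three.

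| Change in stool form | A and D | B, C and per BM |
|---|---|---|
| type 2 to type 4 | (8 − 4)/7 = +0.57 | 4 − 2 = +2.00 |
| type 2 to type 7 | (14 − 4)/7 = +1.43 | 7 − 2 = +5.00 |
| type 4 to type 7 | (21 − 12)/7 = +1.29 | 7 − 4 = +3.00 |

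Every entry is positive, so every one is labelled improvement. Under every reading, reaching watery stool from type 2 scores 2.5 times as much as reaching ideal stool (5/2 = 2.5; 1.43/0.57 ≈ 2.5).

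**Frequency.** Stool form is held at type 2 throughout. The baseline is two BMs on separate days.

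| Change in frequency | A | B | C | D | Per BM |
|---|---|---|---|---|---|
| 2 to 4 days with one BM each | 8/7 − 4/7 = +0.57 | 8/4 − 4/2 = 0.00 | 0.00 | 8/7 − 4/7 = +0.57 | 0.00 |
| two BMs on each of the same 2 days | 8/7 − 4/7 = +0.57 | 8/2 − 4/2 = +2.00 | 0.00 | 4/7 − 4/7 = 0.00 | 0.00 |

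The score moves with frequency under A, B and D in at least one scenario. It does not move under C or per BM.

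**The two parts are independent.** Dividing by BMs removes the frequency effect but leaves +3.00 for type 4 to type 7.

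**The case against.** On direction, the best defence is that these patients are constipated, and that Section 4.2 excludes conditions associated with diarrhea or intermittent loose stools, so upward movement will often be real improvement. The sentence also only labels a sign: removing it changes no computed mean and no test. Both points are fair. The examples are whole-period shifts to the end of the scale, and nothing in the documents says how often they would occur. But the label governs how a group difference is interpreted, and the entry criteria do not guarantee a baseline of type 1 or 2.

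A reader might infer that the plan hides diarrhea. It does not. Adverse events are the primary endpoint (Section 10.1), and Section 11.2.1 additionally analyses related events mapped to the GI tract. Section 1.4 calls 25 mg well tolerated and gives any GI event as 53% against 48% on placebo.

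A reader might also infer that the plan divides per-BM ratings by days, so that BSS is necessarily confounded with frequency. The text does not say that. It speaks of daily values, in wording close to that for daily pain scores and opioid dose, and a natural reading is one value per day over days that have a rating (reading C). The zero-not-missing rule in Section 10.2.1.1 concerns BM counts.

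Some striking figures therefore hold only conditionally. Two type-4 BMs a day for 4 days give (2 × 4 × 4)/4 = 8, off the 1-7 scale, only if ratings are added within a day; a daily mean gives 4. Type-4 stools on 3 against 6 of 7 days give 12/7 = 1.7 against 24/7 = 3.4 only if days without a BM are counted. What stands is that the text neither imposes nor excludes these readings.

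Nor is the straining denominator simply the correct one. Five type-7 BMs on one day plus one type-3 BM on each of three days give 44/8 = 5.5 per BM, but (7 + 3 + 3 + 3)/4 = 4.0 as a mean of daily means. The choice is one of weighting.

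**Conclusion.** The direction rule is wrong as written. It contradicts Section 6.2.5 under all four readings and the per-BM form, crediting type 4 to type 7 with up to +3 and ranking watery above ideal stool from a type-2 start.

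The denominator finding is narrower: the daily value and the days counted are undefined, and three of the four readings let BM frequency move the score, by +0.57 to +2.00 in the assumed diaries. The documents do not establish that the score will be confounded.

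The consequence is limited to one secondary efficacy outcome in a pilot. The responder definition in Section 10.2.1.1 uses spontaneous BMs only, and the adverse event analyses do not use BSS. The point should be corrected before analysis, but it does not threaten the primary aim.

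**What to change.** In Section 10.2.1.4:

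1. Delete the sentence that labels positive changes as improvement.
2. For each patient and period, derive the percentage of rated BMs in types 1-2, 3-4 and 5-7. Summarise and compare these between groups. Define improvement as a rise in types 3-4, and report types 5-7 alongside.
3. Set periods with no rated BM to missing, and report how many patients this affects in each group.
4. If a mean is also kept, compute it either over rated BMs or as daily means over days with a rated BM. State which in advance, and attach no direction of benefit.

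Align the mention of BSS in Section 11.2.2 with this.

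The ratings are already collected at each BM, so the cost is text and one derivation. There is a modest downside: percentages are coarse when few BMs are recorded, especially in the 7-day baseline, where fewer than 3 spontaneous BMs is itself a qualifying symptom. A patient with no rated BM at baseline has no change score. Those patients may be among the most constipated, which is why the count of missing periods should be shown.
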